3.9 Post-Treatment Procedures

No more patients will undergo post-treatment procedures as of 06/18/2018.

The following procedures will be performed following the DEB-TACE procedure:

- Cone Beam CT of the liver will be performed to determine distribution and density of the beads in the tumor.
- Lactate whole blood venous will be collected 2 hours post-procedure.
- Adverse events monitoring

Patients will be discharged the same day if clinically indicated. Patients may be admitted to the hospital after the embolization procedure if clinically indicated.

3.10 Follow-Up Procedures

As of 06/18/2018, patients already enrolled will only be followed for ongoing, related adverse events. This is outlined further in Section 4.6.

A follow-up phone call visit is being added to assess adverse events. Upon approval of this protocol, currently enrolled patients will be mailed a letter explaining the change in study status (Appendix 6.5) and be contacted via telephone (Appendix 6.6). The study closeout letter will be sent certified with return receipt requested. A copy of the letter sent and mailing receipt will be filed in the patient binder. The phone call will ensure all possible existing adverse events have been captured and provide an opportunity to assess ongoing, related adverse events before study completion. Only patients still being monitored for adverse events during the first six months post initial treatment procedure will receive this phone call. Patients outside of this first 6 month window will not be called as adverse event data collection for new adverse events has already ceased. The phone call will be documented in the communication log in the patient binder.

3.11 Re-Treatment

No patient data collection or follow-up relative to re-treatment will occur after 06/18/2018.

Patients may be retreated with DEB-TACE if clinically indicated prior to the three month endpoint.

Retreatment DEB-TACE procedures will be performed in accordance with the study treatment procedures described above. If patients have residual disease at one month they will be included as 1 month data but will not be evaluated for six month recurrence. They will be assessed only for 1 month response and then will be treated according to standard of care. The 1 month response evaluation will be 1 month counted from the retreatment procedure, not the initial procedure. This excludes only the downstaging population which will be evaluated on successful vs. unsuccessful downstaging to within Milan as a binary finding.

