2.4.3 Primary Endpoints

1. Tumor response (modified RECIST criteria) at 1 month as shown by contrast enhanced CT/MRI. (Note: Tumor response will be determined on a per-treated lesion basis.)
2. Local recurrence rate (LRR) at 6 months as shown by contrast enhanced CT/MRI
3. Absolute Tumor enhancing maximum diameter at 1M and 6M.

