2.4.4 Secondary Endpoints

1. Tumor response (mRECIST criteria) at 3 and 6 months as shown by contrast enhanced CT/MRI
2. Successful downstage to Milan criteria or UCSF criteria
3. Time to progression
4. Treatment-related toxicity
5. Change in Liver Functions Tests
6. Change in Quality of life
7. Changes in AFP levels

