4.5.5 Local Recurrence

Local recurrence will be evaluated in subjects at the six month post procedure follow-up visit. Subjects will continue to be evaluated every three months thereafter by CT/MRI until liver transplantation or death.

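### The 6-month local recurrence comparison is restricted to patients without residual disease at 1 month, an outcome the catheter is meant to change, while the power table counts every patient

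*Combined protocol and SAP*

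**What the plan says.** Section 2.4.3 lists as primary endpoints the 1-month mRECIST response, "Local recurrence rate (LRR) at 6 months as shown by contrast enhanced CT/MRI" and "Absolute Tumor enhancing maximum diameter at 1M and 6M". Section 2.4.4 adds "Tumor response (mRECIST criteria) at 3 and 6 months as shown by contrast enhanced CT/MRI". Section 4.5.5 states: "Local recurrence will be evaluated in subjects at the six month post procedure follow-up visit". None of these limits the 6-month assessment to responders, and neither does the 6-month size-change model in 4.4.

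Section 3.11 does. Patients with residual disease at 1 month contribute 1-month data but "will not be evaluated for six month recurrence". The next sentence is broader: "They will be assessed only for 1 month response and then will be treated according to standard of care". Two further sentences qualify the rule:

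- On timing after retreatment: "The 1 month response evaluation will be 1 month counted from the retreatment procedure, not the initial procedure".
- On scope: "This excludes only the downstaging population which will be evaluated on successful vs. unsuccessful downstaging to within Milan as a binary finding".

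Section 4.3 sizes the study on LRR, with 100 controls and 50 Surefire patients as denominators. Section 4.4 compares the proportions with Fisher's exact test. No all-patient analysis of the 6-month recurrence outcome is planned.

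**The concern.** One-month response is the effect named in the hypothesis (2.4.2) and a primary endpoint. Under 3.11 it also decides who enters the 6-month LRR comparison, so the two groups are compared after selection on something the catheter is meant to alter. If the new catheter clears harder tumours, it brings higher-risk patients into its own recurrence denominator. LRR among cleared patients can then fail to show a real benefit, or move slightly against it.

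Two other things are at stake. The power table describes a denominator that the retreatment rule may not deliver. And if 3.11 is read literally for tumour size, the 6-month size model would be fitted to patients with no enhancing tumour left at 1 month, and would mostly reflect baseline size and regrowth.

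**Working it through.** **Inputs.** Historical table in 2.4.1: CR at 1 month 48/152 overall, 33/84 for 0-3 cm, 15/60 for 3-7 cm, 0/8 for >7 cm; 1/23 for tumours of 5 cm or more. Six-month status of the 48 complete responders: 23 without recurrence, 20 with recurrence, 5 lost. Recurrence among those with known status: 12/31 (0-3 cm) and 8/12 (3-7 cm). Planned sizes: 100 and 50 (3.3). Power assumptions: control LRR 30%, alpha 0.05 (4.3).

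**Reproducing the stated power.** For 30% vs 10%, 100 vs 50, two-sided, the arcsine approximation with continuity correction (Walters) gives 0.778 and exact enumeration with a doubled one-tail p-value gives 0.780. Both match the stated 0.78. Exact enumeration with the minimum-likelihood p-value gives 0.814.

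**Evaluable patients if the rule applies to everyone in both arms.**
- Controls: 100 x 48/152 = 31.6, about 32.
- Surefire: 50 x 48/152 = 15.8, about 16.

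**Power for 30% vs 10%.**

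| Calculation | 100 vs 50 | 32 vs 16 |
|---|---|---|
| Walters | 0.78 | 0.24 |
| Exact, doubled one-tail | 0.78 | 0.21 |
| Exact, minimum-likelihood | 0.81 | 0.27 |

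If the Surefire CR rate were 40% or 50% (assumptions; n = 20 or 25) against 32 controls, minimum-likelihood power would be 0.30 or 0.40. The historical recurrence rate among complete responders is also not 30%: it is 20/48 = 41.7%, or 20/43 = 46.5% of those followed.

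**Direction of the conditional comparison.** Hold recurrence within each size band at 12/31 = 0.387 and 8/12 = 0.667, and change only the CR counts a (0-3 cm) and b (3-7 cm). Conditional LRR = (0.387a + 0.667b)/(a + b). Durable CR = (a + b - recurrences)/152.

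| Scenario | a, b | Conditional LRR | Durable CR |
|---|---|---|---|
| Historical | 33, 15 | 47.4% | 16.6% |
| Equal relative gain (x1.5) | 49.5, 22.5 | 47.4% | 24.9% |
| +10 points in each band | 41.4, 21 | 48.1% | 21.3% |
| +20 points in each band | 49.8, 27 | 48.5% | 26.0% |
| CR 50% in each band | 42, 30 | 50.4% | 23.5% |

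Durable CR rises in every scenario, while conditional LRR is unchanged or up to 50.4 - 47.4 = 3.0 points higher.

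**All-treated alternative.** Control value: 23/152 = 15.1%, with lost patients counted as failures. Exact (minimum-likelihood) power for 100 vs 50 is 0.52, 0.75 and 0.90 for Surefire values of 30%, 35% and 40%. With the doubled p-value it is 0.48, 0.71 and 0.88.

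**Which endpoints are affected.**
- LRR: excluded in terms by 3.11.
- Six-month diameter and 3- and 6-month mRECIST: 3.11 read literally stops assessment; 2.4.3, 2.4.4 and the size model in 4.4 carry no restriction. The sections contradict each other.
- Time to progression: 4.4 and 4.5.6 follow all subjects on three-monthly scans.
- Downstaging: exempt under 3.11.

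**The case against.** Recurrence presupposes a tumour that first cleared, so restricting it to complete responders follows from the term, and 2.1.4 and 2.4.1 use it that way. That stands. The fault is using the restricted rate as the between-arm test with no all-patient comparison beside it.

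A reader might infer that all 6-month primary and secondary endpoints exist only for complete responders, and that 68% of patients (104/152) are simply dropped. The documents do not support that. Time to progression and downstaging are planned without the restriction, and for diameter and mRECIST the text conflicts with itself. The size of the exempt group is unknown: 1.2 and 2.4.1 describe patients outside Milan, while inclusion criterion 3 in 3.5.2 also admits patients within Milan. The restarted 1-month clock leaves open whether a patient who clears after retreatment enters the 6-month set. Section 3.11 does not say that the rule applies to controls, and 2.4.1 tabulates later status for the 77 historical partial responders. The exemption or re-entry would raise the 32 and 16.

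A reader might also infer that the comparison will point the wrong way. The figures show only that it can. The shift is 0 to about 3 points, depending on the pattern of CR gain. A relative reduction of about 6% in recurrence within bands cancels the largest case (1 - 47.4/50.4). The size gradient rests on 12/31 vs 8/12 (Fisher p = 0.17; exact 95% interval for 8/12 is 35% to 90%).

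**Conclusion.** The concern holds for LRR. Outside a downstaging population whose extent is undefined, entry to the comparison that sets the sample size depends on a post-treatment outcome, and nothing in 4.4 addresses this. If the rule applies to all patients in both arms at the historical CR rate, evaluable numbers fall to about 32 and 16. Power for 30% vs 10% falls to 0.27 by the minimum-likelihood exact test (0.24 by the approximation that reproduces the plan's 0.78). These are figures for one reading of 3.11, not a forecast. They also treat the historical counts as patients, although 2.4.3 scores response per treated lesion.

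The possible masking or reversal is real in principle but modest in the plan's own data: conditional LRR flat to about 3 points worse while durable complete response improves, assuming unchanged recurrence within size bands. For 6-month diameter and mRECIST, the finding is a contradiction to reconcile, not a settled exclusion.

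**What to change.** 1. In 3.11 and 4.4, define one 6-month analysis set and apply it identically to both arms. State who belongs to the exempt downstaging population, and whether patients who clear after retreatment enter the set.
2. Make the between-arm comparison complete response at 1 month without local recurrence by 6 months, with all treated patients in the denominator (control 23/152 = 15.1%, lost counted as failure). State in advance how transplant, death and loss to follow-up are counted.
3. Report LRR among complete responders as descriptive, and restate its power in 4.3 on the evaluable denominator.
4. Reconcile 3.11 with 2.4.3, 2.4.4 and 4.4. For 6-month diameter and mRECIST, use the scans available for all patients regardless of 1-month response.

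The cost is mainly wording and reanalysis of data already held. There are three limits. Six-month values will include the effect of retreatment. Three-monthly scans are described for study subjects (4.5.6), so their availability in controls has to be checked. Follow-up visits and data entry stopped on 18 June 2018 (3.4), so 6-month data not collected by then cannot be recovered, and the report should say how many patients this affects.

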2.4 Study Objectives

2.4.1 Purpose

The purpose of this study will be to prospectively evaluate the outcomes of patients with hepatocellular carcinoma (HCC) who undergo DEB-TACE with the Surefire Precision Infusion System for intentional effect of down-staging patients to OLT.

Patients with HCC and who are being evaluated for liver transplantation but outside Milan criteria and meet the eligibility criteria will be enrolled in the prospective single arm study.

Results of the prospective cohort will be compared to matched historical control patients who were previously treated with DEB-TACE, delivered with standard endhole catheters. This includes all patients treated at the University of Colorado since 2009 treated with 100-300 micron beads for whom follow-up is available.¹ The data are as follows.

	1-Month Response						
	[name] Criteria				Vesselle, G., et al. (2015) Range Criteria		
	0-3 cm	3-7 cm	>7 cm	Total	<5 cm	>=5 cm	Total
Count	84	60	8	152	129	23	152
Range	1.3-3.0 cm	3.2-7.0 cm	7.6-17.0 cm	1.3-17.0 cm	1.3-4.8 cm	5.0-17.0 cm	1.3-17.0 cm
Number Complete Response	33	15	0	48	47	1	48
Percentage Complete Response	39.29%	25.00%	0.00%	31.58%	36.43%	4.35%	31.58%
Number Partial Response	32	39	6	77	58	19	77
Percentage Partial Response	38.10%	65.00%	75.00%	50.66%	44.96%	82.61%	50.66%
Number Stable Disease	14	4	1	19	17	2	19
Percentage Stable Disease	16.67%	6.67%	12.50%	12.50%	13.18%	8.70%	12.50%
Number Progressive Disease	5	1	1	7	6	1	7
Percentage Progressive Disease	5.95%	1.67%	12.50%	4.61%	4.65%	4.35%	4.61%
Number Lost To Follow-up*	0	1	0	1	1	0	1
Percentage Lost To Follow-up*	0.00%	1.67%	0.00%	0.66%	0.78%	0.00%	0.66%
Total	84	60	8	152	129	23	152

¹ We have robust follow-up on these patients, which is the main reason that we are intending to use this historical comparator.

	6-Month Recurrence (Complete & Partial Response)						
	[name] Criteria				Vesselle, G., et al. (2015) Range Criteria		
	0-3 cm	3-7 cm	>7 cm	Total	<5 cm	>=5 cm	Total
Patients with Complete Response at 1-month	33	15	0	48	47	1	48
Number Lost To Follow-up at 6-months	2	3	0	5	5	0	5
Percentage Lost To Follow-up at 6-months	6.06%	20.00%		10.42%	10.64%	0.00%	10.42%
Number No Recurrence at 6-months	19	4	0	23	23	0	23
Percentage No Recurrence at 6-months	57.58%	26.67%		47.92%	48.94%	0.00%	47.92%
Number Recurrent Disease at 6-months	12	8	0	20	19	1	20
Percentage Recurrent Disease at 6-months	36.36%	53.33%		41.67%	40.43%	100.00%	41.67%
Subtotal	33	15	0	48	47	1	48

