Patients with Partial Response at 1-month	32	39	6	77	58	19	77
Number Transplanted	5	3	0	8	7	1	8
Percentage Transplanted	15.63%	7.69%	0.00%	10.39%	12.07%	5.26%	10.39%
Number Continue TACE to Complete Response	4	0	0	4	4	0	4
Percentage Continue TACE to Complete Response	12.50%	0.00%	0.00%	5.19%	6.90%	0.00%	5.19%
Number Continue TACE to Partial Response	6	12	4	22	15	7	22
Percentage Continue TACE to Partial Response	18.75%	30.77%	66.67%	28.57%	25.86%	36.84%	28.57%
Number Continue TACE to Stable Disease	1	5	0	6	2	4	6
Percentage Continue TACE to Stable Disease	3.13%	12.82%	0.00%	7.79%	3.45%	21.05%	7.79%
Number Continue to Progressive Disease	12	10	0	22	21	1	22
Percentage Continue to Progressive Disease	37.50%	25.64%	0.00%	28.57%	36.21%	5.26%	28.57%
Number Continue TACE unknown status	3	3	0	6	5	1	6
Percentage Continue TACE unknown status	9.38%	7.69%	0.00%	7.79%	8.62%	5.26%	7.79%
Number Change Tx	1	4	2	7	2	5	7
Percentage Change Tx	3.13%	10.26%	33.33%	9.09%	3.45%	26.32%	9.09%
Number Deceased by 6-months	0	2	0	2	2	0	2
Percentage Deceased by 6-months	0.00%	5.13%	0.00%	2.60%	3.45%	0.00%	2.60%
Subtotal	32	39	6	77	58	19	77

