For the outcome of tumor response measured as the change in enhancing tumor size (pretreatment – post treatment) we will evaluate changes at 1 month and 6 month separately. We will calculate the difference in tumor enhancement size at 1 month and 6 months using enhancement size at initial treatment as the reference group (i.e. we will have two continuous outcomes which can be positive or negative values). The analyses are exactly parallel for 1 month and 6 month outcomes. We will describe the approach for 6 months. We will fit a general linear model with Kenward-Roger denominator degrees of freedom. The outcome will be the first-differenced 6 month tumor enhancement size. We will use a random intercept to account for correlation between lesions within a given patient. The independent variables will include catheter type, age and sex. We will test the null hypothesis of no association between catheter type and change in tumor enhancement size. In the case that this model fails to converge, or in the case that most patients have only one tumor, we will use an alternative approach. In this alternative approach we will sample one lesion per patient and use ordinary least squares regression and include age and sex as covariates with catheter type as the primary predictor of interest. We will test the null hypothesis of no association between change in tumor enhancement size and catheter type. Should this model also fail to converge, we will simplify further and use a paired t-test comparing initial and 6 month tumor enhancement sizes in a sampled data set (i.e. one tumor per patient), or we will use a Wilcoxon-Mann-Whitney test if the sizes are skewed. We will test the null hypothesis of no association between catheter and tumor enhancement size change.

For the outcome of time to progression, we will quantify the number of weeks from treatment until tumor progression. Failures (or events) will be defined as progression of the tumor per CT examination or AFP level and extrahepatic disease by CT examination, or death due to complications related to the tumor. Censored observations will be defined as patients who we did not observe tumor progression, patients who were lost to follow up, or patients who had a

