4.5.6 Time to Progression

Time to progression will be tracked as a secondary measure based on the standard of care CT/MRI that all subjects will receive every three months as a requirement to remain on the liver transplant waitlist.

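### 6-month tumour size: section 3.11, read literally, drops Surefire patients with residual disease at one month, and nothing drops the matching controls

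*Combined protocol and SAP*

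**What the plan says.** Section 3.11 sets two rules for patients whose tumour is not cleared at one month. They are left out of the six-month recurrence evaluation, and then: "They will be assessed only for 1 month response and then will be treated according to standard of care". The section ends by excepting the downstaging population, which gets a yes/no result on reaching Milan. It does not say whether that group's 6-month size is used.

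Section 2.4.3 lists as its third primary endpoint "Absolute Tumor enhancing maximum diameter at 1M and 6M". The summary in 1.2 names only one-month response and local recurrence as primary. Section 2.4.4 adds "Tumor response (mRECIST criteria) at 3 and 6 months as shown by contrast enhanced CT/MRI".

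Section 4.4 says of the size analyses "The analyses are exactly parallel for 1 month and 6 month outcomes", and for six months "The outcome will be the first-differenced 6 month tumor enhancement size". The model has catheter type, age and sex as predictors. No analysis set is given for six months, and no rule for patients covered by 3.11.

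The control data in 2.4.1 follow two groups to six months: the 48 one-month complete responders, and a separate block headed "Patients with Partial Response at 1-month" with 77. No text says whether 3.11 governs the historical controls.

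**The concern.** 3.11 is written for patients treated under the protocol. Followed to the letter, the Surefire side of the 6-month size test would hold mainly patients whose tumours had lost all enhancement at one month. The control side has no such filter. Patients selected for early complete response tend to have less viable tumour later, whichever catheter was used, so part of any difference could come from who is counted.

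Applying the rule to both arms removes that imbalance when the two devices are equal. It still conditions on a post-treatment result: if Surefire clears more tumours at one month, the two groups of complete responders no longer contain similar tumours. Because the text does not settle the set, the choice could be made after the results are seen. Section 4.3 also says the data will be used to plan a multicentre trial.

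**Working it through.** **The plan's own figure.** Power is stated only for local recurrence: 0.07, 0.21, 0.47 and 0.78 for 30% against 25, 20, 15 and 10%, with 100 controls and 50 Surefire patients. Exact enumeration of Fisher's test (doubled one-tail p-value, two-sided 0.05) gives 0.066, 0.197, 0.459 and 0.780, so the figures reproduce. No power is stated for 6-month size.

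**Share removed (control table, 2.4.1).** Partial 77 + stable 19 + progressive 7 = 103; 103/152 = 67.8%. Complete responders are 48/152 = 31.6%, and one patient was lost. If Surefire had the control response rate, 50 × 48/152 ≈ 16 patients would remain; at an assumed 50-60% complete response, 25-30.

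**Analysis sets the text allows.** Detectable difference at 80% power = (1.96 + 0.84) × √(1/n₁ + 1/n₂), in SD units.

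| Reading of 3.11 | Controls | Surefire | Detectable difference |
|---|---|---|---|
| Excludes nobody from size | 100 | 50 | 0.49 SD |
| Surefire only; controls = complete + partial responders (100 × 125/152) | 82 | 16 | 0.77 SD |
| Both arms, complete responders (100 × 48/152) | 32 | 16 | 0.86 SD |

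**Illustration of the second row with no device effect.** Six-month status is known for 43 complete responders (48 − 5 lost) and 54 partial responders (4 complete, 22 partial, 6 stable, 22 progressive). The table has no diameters, so these are assumptions:
- Mean baseline is the midpoint of each size range: 2.15, 5.10 and 12.30 cm.
- Enhancing diameter at six months, as a share of baseline, is 50% at recurrence, 50% for partial response, 100% for stable disease and 120% for progression.

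Change is baseline minus six months, as in 4.4.
- Complete responders: 19 × 2.15 + 12 × 1.075 + 4 × 5.10 + 8 × 2.55 = 94.55; 94.55/43 = 2.20 cm.
- Partial responders: 4 × 2.15 + 6 × 1.075 − 12 × 0.43 + 12 × 2.55 − 10 × 1.02 + 4 × 6.15 = 54.89.
- Both groups: (94.55 + 54.89)/97 = 1.54 cm.
- Artefact: 2.20 − 1.54 = 0.66 cm in Surefire's favour.

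**Range.** Let the shares at recurrence, partial response and progression vary over 25-100%, 30-70% and 100-150%.
- At 25%, 70%, 150%: 111.20/43 − 118.39/97 = 2.59 − 1.22 = 1.37 cm.
- At 100%, 30%, 100%: 61.25/43 − 156.16/97 = 1.42 − 1.61 = −0.19 cm.

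**Exempt share q.** This treats exempt patients as a random part of the arm whose 6-month size is used. The Surefire mean becomes [(1 − q) × 94.55 + q × 149.44] / [(1 − q) × 43 + q × 97]. At q = 0.5 it is 122.0/70 = 1.74 cm, an artefact of 0.20 cm. At q = 1 it is zero.

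**False-positive rate.** A simulation used 6000 runs, a t-test, one lesion per patient, and the patients with known status: 50 × 43/152 ≈ 14 against 100 × 97/152 ≈ 64. Under the central assumptions p < 0.05 occurred in 19% of runs; over the range, in 2% to 71%; with half the arm exempt, in 6%. With the same set in both arms it was 4.5% to 5.3%.

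**The case against.** The strongest reply is that this is an omission and not a contradiction. "The analyses are exactly parallel for 1 month and 6 month outcomes" describes the model, not who enters it. The quoted sentence in 3.11 follows one about recurrence and can be read as completing it. Section 4.5.6 mentions "standard of care CT/MRI that all subjects will receive every three months as a requirement to remain on the liver transplant waitlist", which shows that later scans were expected but not which analyses they enter. All of this stands. It does not remove the point, because the word *only* in 3.11 is unqualified and 4.4 defines no 6-month set.

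A reader might infer that the plan sets Surefire complete responders against control complete plus partial responders. The documents do not say so. The 2.4.1 tables are descriptive, report recurrence for complete responders only and hold no size data. An unrestricted control group would also include the 26 patients with stable or progressive disease, for whom no 6-month status is given.

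The exemption matters too. Sections 1.2, 2.4.1, 2.4.2 and 3.5.1 describe a downstaging population, so the exempt share could be large. Inclusion criterion 3 also admits patients within Milan or UCSF limits, so it need not be everyone. Exempt patients are defined by tumour burden, so treating them as a random subset is a simplification.

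Finally, the trial is a closed pilot, 1.2 does not list size as primary, and the sample size rests on local recurrence. These facts lower the weight of the point.

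**Conclusion.** The point holds in limited form. Taken literally, 3.11 removes patients with residual disease at one month from the Surefire 6-month size analysis, about two thirds of an arm that responds like the controls. No text applies the same rule to controls, so selection alone could favour Surefire.

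The two-thirds figure assumes the control response rate. It treats the table counts as patients although response is judged per lesion, and it ignores that 3.11 restarts the one-month clock at retreatment.

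The size of the bias cannot be fixed from the documents. The range of -0.2 to 1.4 cm depends on assumed diameters, the assumed control set and nobody being exempt; even its sign is open, and it is smaller or nil if many are exempt. A reader might take 0.66 cm and 19% as the expected error, but they describe one assumed scenario. The same applies to the tumour-free proportions, 23/43 (53.5%) against 27/97 (27.8%): that contrast uses the same assumed sets, and tumour-free status among responders is not an endpoint of the plan. Leaving these patients out of local recurrence is stated in 3.11 and is not disputed here.

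**What to change.** Before any comparison is run:

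- **3.11:** limit the exclusion to six-month recurrence, and delete the clause confining these patients to the one-month assessment.
- **4.4:** state that the 6-month size and the 3- and 6-month mRECIST analyses use every treated patient with a scan at that time, in both arms, whatever the one-month response or retreatment.
- **Fallback:** if 6-month data for patients with residual disease were not entered before 06/18/2018, restrict both arms to one-month complete responders and label the result as conditional on response. Do not use different sets by arm.
- **Reporting:** give, per arm, how many had residual disease at one month and how many of these have 6-month data.

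This costs one edited sentence in 3.11, a short addition to 4.4 and a few counts. It needs no new data collection or entry, so it fits the closure terms. The all-treated set credits later treatment to the first catheter. The fallback would keep about 14 of 50 Surefire patients and 28 of 100 controls (43/152 of each, at control rates) and compares groups selected on a post-treatment result.

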2.4.2 Hypothesis

Delivery of DEB-TACE with the Surefire Precision Infusion System in patients with HCC who are being considered for liver transplant and are being treated for the purpose of tumor down-staging results in improved tumor response (mRECIST criteria) at 1 month as shown by contrast enhanced CT/MRI as compared to matched historical control patients who received DEB-TACE delivered with a standard endhole catheter.

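### Section 3.11 restarts the 1-month response clock for retreated Surefire patients, sets no clock for the historical controls, and leaves unclear whom the restart covers

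*Combined protocol and SAP*

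**What the plan says.** Four statements in Section 3.11 bear on the 1-month reading.

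- Retreatment is allowed: "Patients may be retreated with DEB-TACE if clinically indicated prior to the three month endpoint".
- Patients with residual disease at one month count in the 1-month data but not in six-month recurrence: "They will be assessed only for 1 month response and then will be treated according to standard of care".
- The clock restarts: "The 1 month response evaluation will be 1 month counted from the retreatment procedure, not the initial procedure".
- There is an exemption: "This excludes only the downstaging population which will be evaluated on successful vs. unsuccessful downstaging to within Milan as a binary finding".

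The hypothesis (Section 2.4.2) compares 1-month mRECIST response with matched historical endhole controls, in patients who "are being treated for the purpose of tumor down-staging". Section 2.4.3 lists that response as the first primary endpoint and gives no time zero.

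Section 2.4.1 tabulates the controls. At 1 month there are 48 CR and 77 partial responses (PR) among 152. A second table follows the 77 PRs to six months, with rows such as "Number Continue TACE to Complete Response" (4) and "Number Continue to Progressive Disease" (22).

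On population, Section 2.4.1 says that patients "being evaluated for liver transplantation but outside Milan criteria and meet the eligibility criteria will be enrolled in the prospective single arm study". Inclusion criterion 1 (Section 3.5.2) requires every patient to be under consideration for downstaging, while criterion 3 also admits patients who already meet Milan or UCSF.

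Section 4.4 measures change in enhancing size from the size at initial treatment, at 1 and 6 months, and names a model for it. It names no test for the mRECIST categories.

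**The concern.** A comparison of 1-month response needs the same starting point in both groups. Here one group has a written rule that can move the reading to a month after a second procedure, and the other has no rule. If controls are scored after their first procedure and some Surefire patients after their second, part of any difference reflects extra treatment and extra time, not the catheter.

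The unclear scope adds to this. If the affected group is not fixed in writing, the choice of reading can be made after outcomes are known, on the endpoint that carries the hypothesis.

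**Working it through.** **1. Is the control clock known?** Sections 2.4.1, 2.4.3, 3.3, 4.4 and 4.5.1 give no time zero or retreatment rule for controls. The tables allow only an inference.

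- The 1-month rows add up: 48 CR + 77 PR + 19 stable (SD) + 7 progressive (PD) + 1 lost = 152, and 48/152 = 31.58%, as printed.
- The six-month rows for the PRs add up: 8 + 4 + 22 + 6 + 22 + 6 + 7 + 2 = 77. The 4 who reached CR with continued TACE are therefore inside the 77 and outside the 48.
- Moving those 4 would give 52/152 = 34.2% CR. The printed 31.58% does not include them.

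This points to control scoring before continued TACE. It does not show how many sessions preceded the control scan.

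**2. Whom does the restart cover?**

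| Reading of Section 3.11 | Retreated patients covered | Latest 1-month reading after first procedure |
|---|---|---|
| Restart sentence alone, with the three-month window | any retreated before 3 months | about 3 + 1 = 4 months |
| Restart read with the residual-disease sentences | only those retreated before the first 1-month scan | about 1 + 1 = 2 months |
| Exemption applied to the restart | patients outside the downstaging population: few or none | as above, for those few |

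The exemption sentence does not say whether it lifts the restart, the exclusion from six-month recurrence, or both. Sections 1.2, 2.4.1, 2.4.2 and 3.5.1 and criterion 1 describe everyone as downstaging. Criterion 3 leaves room for a within-Milan subgroup.

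**3. Direction.** Under the first reading, patients scored non-CR would be scored again after more treatment, in the Surefire group only. If only non-CR patients are retreated, each stays non-CR or becomes CR, so the CR rate cannot fall. CR+PR can move either way, because a PR may become SD or PD by the later scan. Under the second reading, the patients have no earlier 1-month score, so nobody is rescored.

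**4. Illustration of size under the first reading.** Assume no device effect, the control distribution in both groups, and a retreated share r of the 104 non-CR patients (152 − 48). The values of r are assumptions; the documents give none.

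CR gain = r × (104/152) × c, where c is the share converted to CR.

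| c and source | r = 0.1 | r = 0.5 |
|---|---|---|
| 4/77, all control PRs | +0.4 points | +1.8 points |
| 4/32, rows naming TACE with known outcome (4 + 22 + 6) | +0.9 | +4.3 |

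For example, 0.5 × 0.684 × 0.125 = 0.043. These conversions come from PRs at six months and are stand-ins.

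The repeat-TACE rates in Section 2.1.4 give larger figures. There are 82 non-CR controls below 5 cm (129 − 47) and 22 at or above (23 − 1). With 40% and 0%, r = 0.5 gives 0.5 × 32.8/152 = +10.8 points. With 55% and 25%, it gives 0.5 × (45.1 + 5.5)/152 = +16.6 points. The text does not make clear which treatment each rate belongs to, so the pairing is an assumption.

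For CR+PR (125/152 = 82.2%) at r = 0.5:

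- Rows naming TACE with known outcome: 6 of 32 fall to SD, so −0.5 × 77 × (6/32)/152 = −4.7 points.
- Adding the 22 who progressed, a row that does not name TACE: −0.5 × 77 × (28/54)/152 = −13.1 points.
- If no PR falls and every retreated SD or PD patient responds: +0.5 × 26/152 = +8.6 points.

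**The case against.** The strongest reply concerns reach. Criterion 1 makes every patient a downstaging candidate, so if the exemption lifts the restart, it may apply to few or no patients and the bias is near zero. Read with the residual-disease sentences, the restart rescores nobody who already has a 1-month score. Sample size rests on local recurrence (Section 4.3), the study describes itself as a pilot, and no test is named for response categories. These points stand and limit the weight of the issue. They do not supply a control clock or settle which reading applies.

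A reader might infer more than the documents support, in three ways.

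- That the Surefire CR rate is certainly inflated. This needs the widest reading and an actual retreatment share.
- That a false-positive rate can be quoted. It cannot, without a retreatment share and a named test.
- That the size-change analysis is restarted too. Section 4.4 anchors its reference to initial treatment, and no text applies the restart to its 1-month time point. If the restart were applied there, the change would span two procedures.

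It can also be said that restarting the controls would restore symmetry. It would, but the endpoint would then be response after a varying number of procedures.

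**Conclusion.** The concern holds in a limited form. Section 3.11 states a restart for Surefire patients, no section states a clock for controls, and the control tables suggest that theirs was not restarted. The 1-month response comparison can therefore rest on different time zeros, and three readings of the restart's scope are open.

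The size is unknown. For CR it runs from about zero upward. For CR+PR the direction is undetermined. The figures above illustrate the widest reading under assumed retreatment shares; they are not estimates or upper bounds. The control clock is inferred from table layout and should be confirmed from the records.

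**What to change.** In Sections 3.11 and 4.4:

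- Define the primary 1-month response, and the 1-month time point of the size change, in both groups from the CT/MRI about 1 month after the index procedure and before any retreatment.
- State one rule, identical in both groups, for patients retreated before that scan, with a sensitivity analysis using their post-retreatment reading.
- Apply the rule to controls from their recorded procedure and scan dates.
- Report post-retreatment response and the proportion retreated separately, beside the controls' continued-TACE rows.
- Reconcile the residual-disease, restart and exemption sentences, and define the downstaging population.

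Stating whether the comparison is CR or CR+PR would be a useful addition, but is not essential to this point.

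The cost is wording plus a check of control dates, using data recorded up to the closure on 18 June 2018. Some early-retreated patients may have no scan before retreatment and will depend on the stated rule and its sensitivity analysis. Retreatment practice and sample size are unchanged.
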